11.3 Site monitoring

Before study initiation, at a site initiation visit or at an investigator's meeting, a Novartis or delegated CRO representative will review the protocol and data capture requirements (i.e. eSource DDE or eCRFs) with the investigators and their staff. During the study, Novartis employs several methods of ensuring protocol and GCP compliance and the quality/integrity of the sites' data. The field monitor will visit the site to check the completeness of subject records, the accuracy of data capture / data entry, the adherence to the protocol and to Good Clinical Practice, the progress of enrollment, and to ensure that study treatment is being stored, dispensed, and accounted for according to specifications. Key study personnel must be available to assist the field monitor during these visits. Continuous remote monitoring of each site's data may be performed by a centralized Novartis or delegated CRO organization. Additionally, a central analytics organization may analyze data & identify risks & trends for site operational parameters, and provide reports to Novartis clinical teams to assist with trial oversight.

The investigator must maintain source documents for each subject in the study, consisting of case and visit notes (hospital or clinic medical records) containing demographic and medical information, laboratory data, electrocardiograms, and the results of any other tests or assessments. All information on CRFs must be traceable to these source documents in the subject's file. Data not requiring a separate written record will be defined before study start and will be recorded directly on the CRFs. The investigator must also keep the original informed consent form signed by the subject (a signed copy is given to the subject).

The investigator must give the monitor access to all relevant source documents to confirm their consistency with the data capture and/or data entry. Novartis monitoring standards require full verification for the presence of informed consent, adherence to the inclusion/exclusion criteria, documentation of SAEs, and of data that will be used for all primary variables. Additional checks of the consistency of the source data with the CRFs are performed according to the study-specific monitoring plan. No information in source documents about the identity of the subjects will be disclosed.

12 Data analysis and statistical methods

Data analysis will be conducted on all subject data at the time the trial ends, or at the time of any interim analysis. Any data analysis carried out independently by the investigator should be submitted to Novartis before publication or presentation.

Full details will be described in Statistical Analysis Plan (SAP) document.

12.1 Analysis sets

For all analysis sets, subjects will be analyzed according to the study treatment(s) received.

The safety analysis set will include all subjects that received any study drug.

Commercially Confidential Information

The PD analysis set will include all subjects who received any study drug and had no protocol deviations with relevant impact on PD data.

Commercially Confidential Information

12.2 Subject demographics and other baseline characteristics

Demographic and other baseline data including Mayo scores/subscores, previous anti-TNF α treatment experience, baseline corticosteroid use/dose and disease duration will be summarized overall and also by treatment group for the safety analysis set.

Commercially Confidential Information

Categorical data will be presented as frequencies and percentages. For continuous data, mean, standard deviation, median, minimum, and maximum will be presented.

12.3 Treatments

The safety set will be used for treatment compliance analysis.

Data for study drug administration and changes in dosage will be listed by treatment group and subject.

Concomitant medications and significant non-drug therapies prior to and after the start of the study treatment will be listed by treatment group and subject.

12.4 Analysis of the primary endpoint(s)

The primary aim of the study is to assess the induction of clinical remission by LYS006 compared to placebo in patients with mild to moderate ulcerative colitis. The PD analysis set will be used for the primary analysis.

12.4.1 Definition of primary endpoint: Clinical remission

The primary endpoint of this study is the clinical remission rate at the End of treatment (EoT) visit (CCI Week 8 for subsequent protocol amendments), i.e. the proportion of the patients who reach the status of clinical remission at the EoT visit.

Clinical remission is defined as a full Mayo score of 2 points or lower, with no individual subscore exceeding one point.

Subjects with early discontinuation for reasons other than COVID-19 before the EoT visit, or use of rescue/prohibited medication during the treatment period, or missing endoscopy score at EoT will be considered failed to reach remission.

Discontinuation prior to the defined treatment period, or subjects who were not able to complete endoscopy at EoT visit due to local COVID-19 related restrictions will be considered as missing data.

12.4.2 Statistical model, hypothesis, and method of analysis

The binary endpoint of clinical remission rate will be modelled with binomial distribution and analyzed via Bayesian approach. The clinical remission rate for the LYS006 group will be given a neutral prior (Kerman 2011), Beta (1/3, 1/3). The clinical remission rate for the placebo group will be given an informative prior derived via the meta-analytic predictive (MAP) approach (Neuenschwander et al 2010 and Schmidli et al 2014). The derivation of this informative prior can be found in the study sample size documentation. This prior is based on the control groups from a number of historical UC trials (Rutgeerts et al 2005, Reinisch et al 2011, Sandborn et al 2012 and Ito et al 2010) and the selection of historical UC studies was based on patient population and the endpoint. The MAP prior for the placebo remission rate will be a mixture of four beta-distributions, Beta (18.9, 167.4), Beta (3.2, 24.2), Beta (1.0, 3.3) and Beta (1,1), with the mixture weights being 0.43, 0.34, 0.03 and 0.2 respectively. The last non-informative component is added to robustify the outcome in case of any difference between within-study placebo group and those from the historical studies.

With the specified priors and the observed remission rates from this study, the posterior distributions for clinical remission rates in LYS006 and placebo will be computed. The posterior probabilities as defined in the dual efficacy criteria below will be provided, along with the posterior remission rates by group and the treatment difference with 90% credible intervals.

The dual efficacy criteria are defined as ("diff" refers to the difference of true remission rates in LYS006 and placebo):

- (1) EoT clinical remission rate better than placebo with high confidence (90%), i.e. Prob (diff > 0) > 90%, AND
- (2) Average magnitude of effect on EoT clinical remission rate > 15% over placebo, i.e. Prob (diff > 15%) > 50%.

12.4.3 Handling of missing values/censoring/discontinuations

In the primary analysis, subjects who discontinue from the study for reasons other than COVID-19 prior to EoT visit, or have received rescue or prohibited medication for the treatment of ulcerative colitis during the treatment period will be considered failed to reach clinical remission. Discontinuation prior to the defined treatment period, or subjects who were not able to complete endoscopy at EoT visit due to local COVID-19 related restrictions will be CCI considered as missing data. Any missing subscore at Week 8 (subsequent protocol amendments) will lead to a non-evaluable clinical remission status and the subject will also be considered failed to reach clinical remission. Reasons for missing Mayo scores or subscores need to be collected to understand the impact of such analysis approach. Imputation methods such as tipping point analysis may be explored.

12.5 Analysis of secondary endpoints

Assessing safety and tolerability of LYS006 in this population is the secondary objective of the study.

12.5.1 Safety endpoints

For all safety analyses, the safety set will be used. All tables, figures and listings tables will be presented by treatment group.

Safety summaries (tables, figures) include only data from the on-treatment period with the exception of baseline data which will also be summarized where appropriate (e.g. change from baseline summaries). In addition, a separate summary for death including on treatment and post treatment deaths will be provided, if there were death during the study. In particular, summary tables for adverse events (AEs) will summarize only on-treatment events, with a start date during the on-treatment period (treatment-emergent AEs).

Adverse events

All information obtained on adverse events will be displayed by treatment group and subject.

The number (and percentage) of subjects with treatment emergent adverse events (events started after the first dose of study medication or events present prior to start of double-blind treatment but increased in severity based on preferred term) will be summarized in the following ways:

- by treatment, primary system organ class and preferred term.
- by treatment, primary system organ class, preferred term and maximum severity.
- by treatment, Standardized MedDRA Ouery (SMO) and preferred term.

Separate summaries will be provided for study medication related adverse events, death, serious adverse events, and other significant adverse events leading to discontinuation.

The number and percentage of subjects with adverse events of infections, CCI will be summarized by treatment.

A subject with multiple adverse events within a primary system organ class/preferred term is only counted once towards the total of this primary system organ class/preferred term.

Summaries will also be provided for the number of adverse events by treatment.

Vital signs

Abnormalities (and relevant orthostatic changes) will be flagged and reported. The subjects with abnormal values will be visualized along with all subjects in overlaid individual plots by treatment group.

ECG

Abnormalities will be flagged and reported. For continuous ECG parameters, the subjects with abnormal values will be visualized along with all subjects in overlaid individual plots by treatment group. Clinically notable events such as those in Exclusion Criteria 24 will be summarized separately by treatment group.

Clinical laboratory evaluations

Shift tables using the low/normal/high classification based on laboratory normal ranges will be used to compare baseline to the worst on-treatment value. For continuous laboratory parameters, the subjects with abnormal values will be visualized along with all subjects in overlaid individual plots by treatment group.

In particular, abnormalities in selected liver, CCI function parameters/events (Section 10.2) will be summarized separately by treatment group. Graphical presentation will be used as needed.

12.7 Interim analyses

12.8 Sample size calculation

[figure not shown]
Approximately a total of 45 subjects are planned to be enrolled, with a randomization ratio of 2:1. Use of historical control data, as described in Section 12.4.2 helps to reduce the within-study control.

12.8.1 Primary endpoint(s)

Figure 12-2 below illustrates the operating characteristics for the design of 45 subjects with 2:1 randomization ratio. The outcome of approximately 50% data is also shown in the same figure. The informative prior for the placebo group is included in the analysis. Assuming the true treatment difference in remission rate is 25% between LYS006 and placebo CCI

, the probability of meeting the dual efficacy criteria, stated in Section 12.4.2, is 86% with the full 45 subjects and 73%, for half the size. If there is no difference between LYS006 and placebo in clinical remission rate, the chance of meeting dual criteria is below 5% as shown in the left hand panel of the figure and the chance of meeting neither criterion is 92%, as shown in the right hand panel.

Figure 12-2 Operating charateristics for current design: 30 on LYS006 vs. 15 on placebo with historical placebo

12.8.2 Secondary endpoint(s)

Not applicable.

13 Ethical considerations and administrative procedures

13.1 Regulatory and ethical compliance

This clinical study was designed and shall be implemented, executed and reported in accordance with the International Conference on Harmonisation (ICH) Harmonized Tripartite Guidelines for Good Clinical Practice, with applicable local regulations (including European Directive

2001/20/EC, US Code of Federal Regulations Title 21), and with the ethical principles laid down in the Declaration of Helsinki.

13.2 Responsibilities of the investigator and IRB/IEC

Before initiating a trial, the investigator/institution must obtain approval/favorable opinion from the Institutional Review Board/Independent Ethics Committee (IRB/IEC) for the trial protocol, written informed consent form, consent form updates, subject recruitment procedures (e.g. advertisements) and any other written information to be provided to subjects. Prior to study start, the investigator is required to sign a protocol signature page confirming his/her agreement to conduct the study in accordance with these documents and all of the instructions and procedures found in this protocol and to give access to all relevant data and records to Novartis monitors, auditors, Novartis Quality Assurance representatives, designated agents of Novartis, IRBs/IECs, and regulatory authorities as required. If an inspection of the clinical site is requested by a regulatory authority, the investigator must inform Novartis immediately that this request has been made.

For multi-center trials, a Coordinating Investigator will be selected by Novartis by the time of Last Patient Last Visit to be a reviewer and signatory for the clinical study report.

13.3 Publication of study protocol and results

The key design elements of this protocol will be registered in a publicly accessible database such as clinicaltrials.gov and as required in EudraCT. In addition, after study completion (*defined as last patient last visit*) and finalization of the study report the results of this trial will either be submitted for publication and/or posted in a publicly accessible database of clinical trial results, such as the Novartis clinical trial results website and all required Health Authority websites (e.g. Clinicaltrials.gov, EudraCT etc.).

13.4 Quality Control and Quality Assurance

Novartis maintains a robust Quality Management System (QMS) that includes all activities involved in quality assurance and quality control, to ensure compliance with written Standard Operating Procedures as well as applicable global/local GCP regulations and ICH Guidelines.

Audits of investigator sites, vendors, and Novartis systems are performed or overseen by Novartis Pharma Auditing and Compliance Quality Assurance (or CRO working on behalf of Novartis), a group independent from those involved in conducting, monitoring or performing quality control of the clinical trial. The clinical audit process uses a knowledge/risk based approach.

Audits are conducted to assess GCP compliance with global and local regulatory requirements, protocols and internal SOPs, and are performed according to written Novartis processes

14 Protocol adherence

This protocol defines the study objectives, the study procedures and the data to be collected on study participants. Additional assessments required to ensure safety of subjects should be administered as deemed necessary on a case by case basis. Under no circumstances including

incidental collection is an investigator allowed to collect additional data or conduct any additional procedures for any purpose involving any investigational drugs under the protocol, other than the purpose of the study. If despite this interdiction prohibition, data, information, observation would be incidentally collected, the investigator shall immediately disclose it to Novartis and not use it for any purpose other than the study, except for the appropriate monitoring on study participants.

Investigators ascertain they will apply due diligence to avoid protocol deviations. If an investigator feels a protocol deviation would improve the conduct of the study this must be considered a protocol amendment, and unless such an amendment is agreed upon by Novartis and approved by the IRB/IEC and Health Authorities, where required, it cannot be implemented.

16.1 Appendix 1: Clinically notable laboratory values

Please refer to the Central Laboratory Manual for a list of clinically significant laboratory values.

## 1 Introduction

### 1.1 Scope of document

The RAP documents contain detailed information to aid the production of Statistics & Programming input into the Clinical Study Report (CSR) for trial “**CLYS006X2202**”.

The Statistical analysis plan (SAP) describes the implementation of the statistical analysis planned in the protocol for the final analysis, as well as the outputs planned for the interim analyses.

### 1.2 Study reference documentation

Commercially Confidential Information

### 1.3 Study objectives

#### 1.3.1 Primary Objective

Primary objective	Endpoint related to primary objective

To assess the induction of clinical remission by LYS006 in patients with mild to moderate ulcerative colitis (UC) compared to placebo

	

Clinical remission rate at Week 8 using the full Mayo score

#### 1.3.2 Secondary Objective

Secondary objective	Endpoints related to secondary objective

To assess safety and tolerability of LYS006 in patients with mild to moderate ulcerative colitis compared to placebo

	

Number and severity of adverse events/ number of subjects with adverse events

Safety and tolerability based on general safety measurements (safety laboratory measurements, vital signs and ECG parameters)

Commercially Confidential Information

Commercially Confidential Information

Commercially Confidential Information

## 1.4 Study design and treatment

This is a randomized, placebo-control, subject and investigator blinded, multicenter, parallel group study in patients with mild to moderate ulcerative colitis (UC).

Approximately 45 patients will be randomized in a 2:1 ratio to one of the following groups:

- Group 1: LYS006 capsules (20 mg BID)
- Group 2: matching placebo (BID)

[Figure 1-1](#) depicts the design of the study, starting from a screening epoch of up to 4 weeks (minimum screening duration of 7 days to enable collection of stool frequency and rectal bleeding subscores), a treatment period of 8 weeks and a follow-up period of 30 days post last administration of study treatment, before the End of Study (EoS) visit. The total duration for each subject in the study will be up to 16 weeks.

[figure not shown]
For the entire duration of the treatment period (8 weeks), subjects will receive twice-daily doses of LYS006 or placebo. Each subject will take 4 capsules to make up to a dose of 20 mg twice a day.

Baseline visit will be Day 1. Baseline and drug administration can be done the same day if all eligibility criteria are met.

Commercially Confidential Information

Commercially Confidential Information

**Figure 1-1** Study design

## 2 First interpretable results (FIR)

Commercially Confidential Information

### 3 Interim analyses

Commercially Confidential Information

## 4 Statistical methods: Analysis sets

For all analysis sets, subjects will be analyzed according to the study treatment(s) received.

The safety analysis set will include all subjects that received any study drug.

Commercially Confidential Information

The PD analysis set will include all subjects who received any study drug and had no protocol deviations with relevant impact on PD data.

The data collected from the subjects      Commercially Confidential Information

Commercially Confidential Information

will be pooled for all the analyses listed in this document.

The analysis sets and protocol deviation codes are related as follows:

**Table 4.1** Protocol deviation codes and analysis sets

Category Deviation code	Text description of deviation	Data exclusion
	Subjects are excluded from all (safety) analysis in case of these protocol deviations:	Exclude subject completely from all (safety) analysis sets
INCL01	Deviation from inclusion criterion 1 (Written informed consent must be obtained before any assessment is performed)	Yes

Category Deviation code	Text description of deviation	Data exclusion
Commercially Confidential Information		
Subjects are excluded from PD analysis in case of these protocol deviations:		
INCL01	Deviation from inclusion criterion 1 (Written informed consent must be obtained before any assessment is performed)	Yes
TRT04	Wrong dose of study drug	Yes
OTH12PA2	Change in Standard of Care treatment	Yes

Commercially Confidential Information

---

If updates to this table are needed, an amendment to the SAP needs to be implemented prior to DB lock.

Commercially Confidential Information

Commercially Confidential Information

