5.1 Inclusion criteria

Subjects eligible for inclusion in this study must meet all of the following criteria:

- 1. Written informed consent must be obtained before any assessment is performed.
- 2. Male and female subjects aged 18-75 years at screening
- 3. Patients diagnosed with UC established at least 3 months prior to screening.
- 4. Patients with mild to moderate UC which is defined by a total Mayo Score between 5 and 10 (inclusive), comprised of the following subscores;
 - Endoscopic subscore: 2 or 3 (determined from central reading of screening endoscopy)
 - Stool frequency subscore: 1-3

- Rectal bleeding subscore: 1-3
- Physician's global assessment subscore: 1-2. Please see the SOM for guidance on completion of Mayo scores
- 5. Disease must extend beyond 15 cm from the anal verge (assessed by screening endoscopy).
- 6. Patients must have responded inadequately or have intolerance to conventional therapy with oral 5-ASA prior to screening, and be willing to continue 5-ASA at a stable dose during the study treatment period. Inadequate response is defined by the following:
 - Active disease despite induction therapy with 5-ASA agents where adequate therapy is a stable oral 5-ASA dose.
 - Adequate therapy is an oral 5-ASA (mesalamine ≤ 4.8 g/day, sulfasalazine ≤ 6 g/day, balsalazide ≤ 7.5 g/day or olsalazine ≤ 3 g/day) with a stable dose administered for at least 4 weeks prior to the screening endoscopy.
 - In addition to oral 5-ASA, oral corticosteroids including oral budesonide are permitted provided the following criteria are met and the patient is willing to continue to continue the medication at a stable dose during the study treatment period
 - o Oral corticosteroids are allowed if the dose is < 10 mg/day with a stable dose administered for at least 4 weeks prior to the screening endoscopy.
 - Oral budesonide is allowed if the dose is $\leq 9 \text{ mg/day}$ with a stable dose administered for at least 4 weeks prior to the screening endoscopy.
- 7. Able to communicate well with the investigator, to understand and comply with the requirements of the study.

5.2 **Exclusion criteria**

Subjects meeting any of the following criteria are not eligible for inclusion in this study.

- 1. Use of investigational drugs within 4 weeks or 5 half-lives of screening, whichever is longer; or longer if required by local regulations.
- 2. Confirmed laboratory findings at screening showing:

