6.2.1.1 Permitted concomitant therapy requiring caution and/or action

Subjects are required to continue to take standard of care treatment (5-ASAs and if relevant oral corticosteroids (max 10 mg per day prednisone or equivalent) or oral budesonide (≤ 9 mg/day)) at a stable dose for four weeks prior to the screening endoscopy until the End of Treatment period.

Subjects on concomitant chronic treatment for hypertension, diabetes and/or other for chronic illness that may not confound the interpretation of study results or put the subject in risk are allowed to continue on their regular treatment regimen but it should be documented in the source document. The investigator must discuss the concomitant medications with the Sponsor on a case by case basis where there is a potential for these medications to alter the efficacy measurements, interfere with the study medication, or interpretation of results.

Hormonal contraception is allowed during the study, and is mandatory if it is the only method of contraception (please refer to inclusion/exclusion criteria).

Administration of paracetamol (acetaminophen) is acceptable, but must be documented.

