6.2.3 Rescue medication

cyclophosphamide, azathioprine

Budesonide with dose > 9 mg/day

Systemic corticosteroids with

dose > 10 mg/day (equivalent

Topical anti inflammatory

treatments (e.g. Topical 5-

medications

aminosalicylic acid (5-ASA) or

metronidazole or ciprofloxacin

Antidiarrheal, antimotility

prednisone)

In cases where the investigator believes rescue medication is necessary, it may be administered but the subject must be discontinued from the study treatment. For example, if a subject's disease is worsening, a corticosteroid dose may be increased or an immunomodulatory agent may be introduced, and the subject should be discontinued from the study treatment.

If the ulcerative condition worsens after the treatment period is finished, any medically indicated rescue medications can be prescribed during the follow up period.

Use of rescue medication must be recorded on the Concomitant medications/Significant nondrug therapies after start of study drug in the (e)CRF.

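### A corticosteroid increase given as rescue counts as non-remission, but SAP Table 4.1 as worded can also remove that subject from the primary analysis set

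*SAP*

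**What the plan says.** **Failure rule.** Protocol 12.4.1 lists "use of rescue/prohibited medication during the treatment period" among the reasons for non-remission. Protocol 12.4.3 says that, in the primary analysis, subjects who "have received rescue or prohibited medication for the treatment of ulcerative colitis during the treatment period will be considered failed to reach clinical remission". SAP 6.1.3.1 repeats the rule. Protocol 6.2.3 leaves rescue to the investigator, requires study treatment to stop, and gives as its example for worsening disease that "a corticosteroid dose may be increased or an immunomodulatory agent may be introduced". It sets no minimum dose.

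**Exclusion rule.** SAP section 4, Table 4.1 has the line "Subjects are excluded from PD analysis in case of these protocol deviations". One of the codes below it is OTH12PA2, "Change in Standard of Care treatment", marked Yes for exclusion. The visible entry has no limit by reason or direction and no exception for rescue. Protocol 12.4 makes the PD set the primary analysis set.

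**What standard of care covers.** Protocol 6.2.1.1: "Subjects are required to continue to take standard of care treatment (5-ASAs and if relevant oral corticosteroids" within stated dose limits, or oral budesonide, at a stable dose until the end of treatment. Inclusion criterion 6 requires subjects to "be willing to continue 5-ASA at a stable dose during the study treatment period".

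**The concern.** A steroid increase for a flare is both rescue and a departure from stable background treatment. Under the first rule the subject stays in the denominator as a failure. Under the second the subject leaves the primary set before the failure rule can act.

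Exclusion would remove a randomised subject because of a post-baseline event that the plan itself treats as failure. It raises the observed remission rate of that subject's arm. If both arms lose the same share of subjects, both rates rise by the same factor, so the larger rate gains more in absolute terms and the difference widens. If placebo loses more, the shift can reverse. With 30 and 15 subjects, the go decision could then depend on how a few deviations are coded.

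**Working it through.** **1. Do the rules overlap?**

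| Event during treatment | Failure rule | OTH12PA2 as visibly worded |
|---|---|---|
| Steroid increase for worsening UC | Yes: named example in 6.2.3 | Yes: oral steroid is standard of care in 6.2.1.1 |
| Budesonide or oral 5-ASA started or raised for UC, within the permitted dose | Only if the investigator treats it as rescue | Yes on the wording |
| Reduction because UC improved | No | Yes on the wording |

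The first row is the firm overlap. The second is conditional. The third is no conflict.

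**2. Inputs.** From protocol 12.4.2: LYS006 prior Beta(1/3, 1/3); placebo prior a mixture of Beta(18.9, 167.4), Beta(3.2, 24.2), Beta(1.0, 3.3) and Beta(1, 1) with weights 0.43, 0.34, 0.03 and 0.2; go if Prob(diff > 0) > 0.90 and Prob(diff > 0.15) > 0.50. From 12.8: 30 v 15 subjects. Assumed, because the documents show neither: the placebo remission rate and the frequency of such treatment changes. The calculation uses no baseline Mayo covariate.

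**3. Formulas.** With y remitters among n:
- LYS006 posterior: Beta(1/3 + y, 1/3 + n − y).
- Placebo posterior: mixture of Beta(a_k + y, b_k + n − y), with weights proportional to w_k · B(a_k + y, b_k + n − y) / B(a_k, b_k).
- Prob(diff > δ) = ∫ f_placebo(q) · [1 − F_LYS006(q + δ)] dq.
- Go probability: sum of the binomial probabilities of all outcomes that meet both criteria.

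**4. The plan's own figures (12.8.1).** At an assumed 11.5% placebo rate and a 25-point difference, go is 86.3% (stated 86%). With no difference, go is 1.9% (stated below 5%) and neither criterion is met in 92.5% (stated 92%).

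**5. Can the choice of rule change a decision?** With placebo 1/15:

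| LYS006 as failures | Prob(diff > 15%) | Two failures excluded | Prob(diff > 15%) |
|---|---|---|---|
| 6/30 | 0.28, no-go | 6/28 | 0.35, no-go |
| 7/30 | 0.43, no-go | 7/28 | 0.51, go |
| 8/30 | 0.59, go | 8/28 | 0.66, go |

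Only the middle row changes. One exclusion is not enough there (7/29 gives 0.47). If two placebo failures also leave, 7/28 v 1/13 gives 0.496, again no-go.

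**6. Average effect.** Hold the all-randomised remission rate p fixed and let a fraction f of an arm be affected, none of them remitting. Counting them as failures leaves the rate at p. Excluding them gives p / (1 − f) in a smaller arm, with the number removed binomial. For f = 5% in both arms, 26.5 / 0.95 = 27.9% and 11.5 / 0.95 = 12.1%, so a 15-point difference becomes 15.8.

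Go probability, failure v exclusion, placebo 11.5%:

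| Affected (LYS006 / placebo) | True diff 15 | True diff 25 | No difference |
|---|---|---|---|
| 5% / 5% | 52 v 55% | 86 v 88% | 1.9 v 2.3% |
| 10% / 10% | 52 v 60% | 86 v 89% | 1.9 v 3.1% |
| 5% / 10% | 52 v 54% | 86 v 87% | 1.9 v 2.1% |

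For the 10% / 10% row, the shift at 15 points is 7.7, 7.5 and 5.9 percentage points at placebo rates of 8%, 11.5% and 15%.

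**7. Direction and extremes.** A separate simulation (40,000 runs, placebo 10%) removes a share of the non-remitters. If 10% of LYS006 and 30% of placebo failures leave, go at a 25-point difference falls from 85% to 82%. If 30% of LYS006 and 10% of placebo failures leave, false go rises from 1.0% to 6.5%. That last case removes about 30 × 0.9 × 0.3 = 8 LYS006 subjects, far more than the table above assumes.

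**The case against.** There is a coherent reading with no conflict. Table 4.1 lists protocol deviations, and rescue under 6.2.3 is permitted as long as study treatment stops, so it need not be coded as a deviation. Once the subject is off study drug, the stable-dose duty has arguably ended. Protocol 12.4.3 and SAP 6.1.3.1 presuppose that rescued subjects are in the analysed set. OTH12PA2 may be meant only for background changes in subjects who stay on study drug. Its full definition is not shown, and text in and after Table 4.1 and in SAP 6.1.3.1 is redacted.

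This is probably the intent, and it bars the stronger inference that the plan does drop rescued subjects. It does not settle the point, because none of it is written as a rule of precedence in the visible text.

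Three other inferences go too far:
- **Every within-cap oral 5-ASA change is caught by both rules.** Oral 5-ASA is not named as rescue, and the visible part of Table 6-2 prohibits only topical 5-ASA.
- **The bias favours LYS006.** The direction depends on which arm loses more failures.
- **The effect is large.** Drawing 28 LYS006 subjects at 26.5% and then adding two forced failures gives 44% v 52%. But the all-randomised rate is then 26.5 × 28/30 = 24.7%, a true difference of 13.2 points rather than 15. Part of that gap is a smaller effect, not the rule.

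**Conclusion.** The point holds for the steroid overlap on the visible text. It extends to budesonide and oral 5-ASA only where the investigator treats the change as rescue. The likely effect is modest: about 3 percentage points of go probability at a true 15-point difference if 5% of each arm is affected, and 7 to 8 points at 10%. False go remains below 5% in those scenarios.

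These sizes rest on an assumed 11.5% placebo rate, assumed incidences, and affected subjects never remitting. The false-go statement is tied to that placebo rate: at 15% it is already 5.6% with nobody excluded. A changed decision needs a result at the boundary. This is worth correcting because the study is small, the remedy is cheap, and otherwise deviation coding could decide a close result.

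**What to change.** Before database lock, amend SAP Table 4.1 and cross-refer to it in SAP 6.1.3.1, for example:

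*Subjects who receive rescue or prohibited medication for UC during the treatment period, including any increase or new start of a corticosteroid, budesonide or 5-ASA given for worsening UC, remain in the PD analysis set and count as non-remission. Exclusion under OTH12PA2 does not apply to them.*

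OTH12PA2 can stay as it is for other changes, such as a reduction on improvement or a change for a reason unrelated to UC. No wider redefinition of the endpoint is needed. If redacted text already sets this precedence, confirming that is enough.

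The cost is a few lines of SAP text and one derivation. The concomitant medication CRF already records dose, start date and reason for therapy (protocol 6.2.1), so no new data are needed. The SAP already provides the route: "If updates to this table are needed, an amendment to the SAP needs to be implemented prior to DB lock". The downside is that observed remission rates may be slightly lower than under exclusion.
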